9.7 Interim Analyses

No interim analyses are planned for this study.

9.8 Multiplicity

No multiplicity adjustment will be required, as there is no formal hypothesis testing.

9.9 Sample Size and Power Calculations

9.9.1 Immunogenicity

This is an estimation study. The study is expected to enroll approximately 160 participants (80 per group). The estimated half-widths of 2-sided 95% CIs for GM Ratios between the Concomitant versus Nonconcomitant Groups for each serotype range between 0.279 to 0.494 ([Table 11](#)), corresponding to a sample size of 80 per group. There is no corresponding power since no hypothesis will be tested.

Table 11 Half-widths of 2-sided 95% CIs for Geometric Mean Ratios by Serotype

Serotype	Expected Coefficient of Variation ^a	Expected Number of Participants Enrolled (per group)	Expected Exclusion from Per-Protocol Population ^a	Half-width of 95% CI for GM Ratio ^b
HPV 6	1.11	80	13%	0.300
HPV 11	1.16	80	13%	0.309
HPV 16	1.17	80	9%	0.304
HPV 18	1.35	80	9%	0.334
HPV 31	1.21	80	10%	0.313
HPV 33	1.20	80	9%	0.309
HPV 45	1.38	80	9%	0.338
HPV 52	1.03	80	9%	0.279
HPV 58	1.10	80	10%	0.293
SARS-CoV-2	2.91 ^c	80	10%	0.494

CI=confidence interval; GM=geometric mean; HPV=human papillomavirus; SARS-CoV-2=severe acute respiratory syndrome coronavirus 2

^a The HPV-specific expected values are based on data from study NCT01984697 (EudraCT: 2013-001314-15).

^b The half-width of 95% CI for GM ratio is calculated at 1-sided Type I error $\alpha=0.025$ under the assumption that the ratio of geometric means in the Concomitant and Nonconcomitant Groups is 1.0.

^c The standard deviation of the SARS-CoV-2 spike protein-specific binding antibody concentrations in natural-logarithm scale was estimated as 1.5. The corresponding coefficient of variation of concentrations in the untransformed scale was calculated as square-root(exp[1.5*1.5] – 1).

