4.2 Scientific Rationale for Study Design

This study was originally designed to have a target enrollment of 400 boys and girls for sufficient power to test hypotheses to demonstrate noninferior immunogenicity of 9vHPV vaccine and mRNA-1273 in the Concomitant Group versus the Nonconcomitant Group. In the setting of the evolving COVID-19 pandemic setting, enrollment has been slower than anticipated. Additionally, the mRNA-1273 vaccine clinical supply will not be available after 1Q2023 to support further enrollment. Therefore, enrollment will conclude in 1Q2023, with expected enrollment of approximately 160 boys and girls 9 to 11 years of age. Participants

will be randomized in an open-label manner to receive 2 preventative vaccinations: 9vHPV and mRNA-1273 vaccines. The study design will allow evaluation of safety and immunogenicity when the first dose of these 2 vaccines are administered concomitantly compared with nonconcomitant administration of the 2 vaccines. The 2-dose series for 9vHPV vaccine is licensed in this age group to be administered 6 to 12 months apart. The 2-dose series for the mRNA-1273 vaccine is administered 28 days apart. As the timing of the 2-dose series differs between the 2 vaccines, this study will generate data to inform coadministration of the first dose of each vaccine. Overall, this design is similar to that used in previous coadministration studies (NCT00988884, NCT01073293) of the 9vHPV vaccine, including coadministration with meningococcal, poliomyelitis, diphtheria, tetanus, and pertussis vaccines [Kosalaraksa, P., et al 2015] [Schilling, A., et al 2015].

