9.1 Statistical Analysis Plan Summary

Key elements of the statistical analysis plan are summarized below; the comprehensive plan is provided in Sections 9.2 to 9.12.

Study Design Overview	A Phase 3, Multicenter, Open-Label Study to Evaluate the Safety and Immunogenicity of 2-dose Regimens of 9vHPV and mRNA-1273 SARS-CoV-2 Vaccines Where the First Dose of Each Vaccine Are Given Concomitantly in Boys and Girls 9 to 11 Years of Age
Treatment Assignment	Study participants will be randomized in a 1:1 ratio between the Concomitant and Nonconcomitant Groups. No stratification will be implemented during randomization.
Analysis Populations	Immunogenicity: Per-protocol population Safety: APaT population
Primary Endpoint(s)	Immunogenicity: 1. cLIA anti-HPV 6, 11, 16, 18, 31, 33, 45, 52, and 58 titers. 2. SARS-CoV-2 spike protein-specific binding antibody concentration. Safety: 1. Solicited injection-site AEs Day 1 through Day 7 postvaccination. 2. Solicited systemic AEs Day 1 through Day 7 postvaccination. 3. SAEs Day 1 through Day 28 postvaccination. 4. Vaccine-related SAEs observed any time during the study.
Key Secondary Endpoints	Immunogenicity: 
Seroconversion to HPV Types 6, 11, 16, 18, 31, 33, 45, 52, and 58 based on cLIA.Seroresponse to SARS-CoV-2 based on SARS-CoV-2 ECL assay.
Statistical Methods for Key Immunogenicity Analyses	Evaluation of primary and secondary objectives will be performed separately for each immunogenicity parameter. Analysis of variance modeling will be used. The response variable is the natural logarithm of the relevant antibody titers and an indicator variable representing the concomitant vaccination group will be a fixed effect. Point estimates of the GMTs/GMC and corresponding within-group 95% CIs as well as geometric mean ratio and corresponding 95% CI of the geometric mean ratio will be derived from the estimate of the fixed effect.
Statistical Methods for Key Safety Analyses	By-treatment group summaries of safety endpoints will be provided in terms of treatment group-specific counts and proportions (or percent) of participants who are cases of particular safety endpoints. Confidence intervals of risk difference (difference in percent or proportions), when provided, will be calculated using the M&N method [Miettinen, O. and Nurminen, M. 1985].
Interim Analyses	No interim analyses are planned for this study.

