9.6 Statistical Methods

9.6.1 Immunogenicity Analysis Methods

9.6.1.1 Estimation of Immune Response Relating to HPV

Anti-HPV titers reported as less than the HPV type-specific LLOQ will be replaced by a numeric value equal to half of the HPV type-specific LLOQ in analyses of immunogenicity.

For each of HPV Types 6, 11, 16, 18, 31, 33, 45, 52, and 58, the primary objective relating to response to HPV vaccination at 4 weeks Postdose 2 will be evaluated. Separately for each HPV type, the GMTs with 2-sided within-group 95% CIs and GMT ratio with corresponding 2-sided 95% CI will be calculated using an analysis of variance model with a response of log individual anti-HPV titers and a fixed effect for the vaccination groups ([Table 9](#)).

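### Table 11 gives half-widths for ln(GM ratio) but labels them as half-widths for the GM ratio itself, which hides the asymmetry of the expected intervals, mainly for SARS-CoV-2

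*Combined protocol and SAP*

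**What the plan says.** Section 9.9.1 opens the precision statement with "The estimated half-widths of 2-sided 95% CIs for GM Ratios between the Concomitant versus Nonconcomitant Groups for each serotype range between 0.279 to 0.494", for 80 participants per group. The title of Table 11 is "Half-widths of 2-sided 95% CIs for Geometric Mean Ratios by Serotype", and its last column header likewise names the GM ratio. Footnote b begins "The half-width of 95% CI for GM ratio is calculated at 1-sided Type I error" and adds that this is done "under the assumption that the ratio of geometric means in the Concomitant and Nonconcomitant Groups is 1.0".

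Section 9.9.1 mentions the log scale only in footnote c, for the spread of one endpoint: "The standard deviation of the SARS-CoV-2 spike protein-specific binding antibody concentrations in natural-logarithm scale was estimated as 1.5". That footnote explains how the SARS-CoV-2 CV of 2.91 was obtained. It does not give the scale of the half-width column.

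The analysis itself is on the log scale. Section 9.6.1.1 says the "GMT ratio with corresponding 2-sided 95% CI will be calculated using an analysis of variance model with a response of log individual anti-HPV titers", and Section 9.6.1.2 applies the same method to SARS-CoV-2. Section 9.1 says that the "geometric mean ratio and corresponding 95% CI of the geometric mean ratio will be derived from the estimate of the fixed effect".

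**The concern.** A CI for a geometric mean ratio from a log-scale ANOVA is symmetric for ln(ratio) and asymmetric for the ratio. One half-width labelled as belonging to the ratio invites the reader to add it to and subtract it from 1.0. Footnote b strengthens that reading by fixing the true ratio at 1.0, a condition a log-scale half-width does not need.

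The study is now an estimation study without power, so Table 11 is all the plan offers on the precision of primary objectives 1 and 2. If its scale is misread, the study appears less able than it is to exclude a reduced response in the Concomitant Group, and more precise than it is on the upper side.

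**Working it through.** **Inputs (Table 11 and its footnotes).** CV and expected exclusion by row; 80 enrolled per group; 2-sided 95% CI; true ratio 1.0.

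**Formula on the natural-log scale.**

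- SD of the log titer: s = sqrt(ln(1 + CV²)).
- Evaluable per group: n = 80 × (1 − exclusion), unrounded: 69.6 at 13%, 72.0 at 10%, 72.8 at 9%.
- Half-width: h = t(0.975, 2n − 2) × s × sqrt(2/n).

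**Two rows in full.**

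- SARS-CoV-2: s = sqrt(ln(1 + 2.91²)) = 1.4993; n = 72; t = 1.9768; sqrt(2/72) = 0.1667. So h = 1.9768 × 1.4993 × 0.1667 = 0.4940 (0.4942 with s = 1.5). Stated: 0.494.
- HPV 52: s = sqrt(ln(1 + 1.03²)) = 0.8504; n = 72.8; t = 1.9766; sqrt(2/72.8) = 0.1657. So h = 0.2786. Stated: 0.279.

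**All rows, with back-transformed limits exp(−h) and exp(h).**

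| Row | h computed | Stated | Expected CI at ratio 1.0 | 1.0 ± stated value |
|---|---|---|---|---|
| HPV 6 | 0.3004 | 0.300 | 0.74–1.35 | 0.70–1.30 |
| HPV 11 | 0.3095 | 0.309 | 0.73–1.36 | 0.69–1.31 |
| HPV 16 | 0.3042 | 0.304 | 0.74–1.36 | 0.70–1.30 |
| HPV 18 | 0.3337 | 0.334 | 0.72–1.40 | 0.67–1.33 |
| HPV 31 | 0.3129 | 0.313 | 0.73–1.37 | 0.69–1.31 |
| HPV 33 | 0.3094 | 0.309 | 0.73–1.36 | 0.69–1.31 |
| HPV 45 | 0.3383 | 0.338 | 0.71–1.40 | 0.66–1.34 |
| HPV 52 | 0.2786 | 0.279 | 0.76–1.32 | 0.72–1.28 |
| HPV 58 | 0.2934 | 0.293 | 0.75–1.34 | 0.71–1.29 |
| SARS-CoV-2 | 0.4940 | 0.494 | 0.61–1.64 | 0.51–1.49 |

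HPV 11 sits on the rounding boundary. Its CV is given to two decimals, and a CV between 1.155 and 1.165 gives h between 0.3086 and 0.3104, which covers the stated 0.309.

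**Alternatives that fail.**

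- A normal quantile in place of t gives 0.298 for HPV 6 and 0.490 for SARS-CoV-2.
- Rounding n to 73 gives 0.333 for HPV 18 and 0.278 for HPV 52.
- Ratio-scale quantities for SARS-CoV-2: distance below 1, 1 − exp(−h) = 0.390; distance above 1, exp(h) − 1 = 0.639; half the total width, (exp(h) − exp(−h))/2 = 0.514 (0.515 with s = 1.5). None is 0.494.

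**Size of the discrepancy.** Across the ten rows the expected lower limit lies 0.243 to 0.390 below 1 and the upper limit 0.321 to 0.639 above 1. Half the total ratio-scale width runs from 0.282 (HPV 52) to 0.514 (SARS-CoV-2), against the stated 0.279 to 0.494. It exceeds the stated value by 0.003 to 0.007 for the HPV types and by 0.02 for SARS-CoV-2.

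**The case against.** Every number in Table 11 is right for the quantity that was computed; only the scale label is missing. Taken strictly as half the total width, the stated values are off by 1% to 2% for the HPV types and 4% for SARS-CoV-2. The larger contrast needs a reader who also assumes symmetry around 1.0, which the plan never asserts. A statistician who has read Sections 9.1 and 9.6.1.1 would probably infer the log scale. Nothing turns on the figures either: there is no hypothesis, margin or precision target, and Section 4.2 ties the sample size to slow accrual and the end of vaccine supply ("enrollment will conclude in 1Q2023, with expected enrollment of approximately 160 boys and girls 9 to 11 years of age").

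Most of this stands, and it limits the weight of the point. It does not remove it. That the scale can be inferred from other sections does not correct a sentence, a title, a header and a footnote that all name the wrong quantity. Half the total width does not match the column either. And a single half-width, even a correct one, does not tell the reader where the two limits of an asymmetric interval lie.

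**Conclusion.** The concern holds. The entries of Table 11 are half-widths of the 95% CI for ln(GM ratio), and Section 9.9.1 presents them as half-widths for the GM ratio. Read as labelled, with symmetry around 1.0, both limits come out too low in every row. For the HPV types the shift is about 0.04 to 0.05 at the lower limit and 0.04 to 0.06 at the upper. For SARS-CoV-2 it is about 0.10 at the lower limit and 0.145 at the upper.

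This rests on Table 11's own CVs and exclusion rates, the lognormal relation between CV and log-scale SD, equal groups and a true ratio of 1.0. It is an error in how precision is described. It should be corrected because no other precision figures are given for primary objectives 1 and 2, but it affects neither the validity of the planned estimates nor the sample size.

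**What to change.** In Section 9.9.1, name the quantity as the half-width of the 95% CI for ln(GM ratio) in the sentence, the Table 11 title, the column header and footnote b. Add a column with the expected limits on the ratio scale at a true ratio of 1.0, using the fourth column of the table above (for example 0.76–1.32 for HPV 52 and 0.61–1.64 for SARS-CoV-2). Relabelling alone would remove the error; the added column spares the reader the back-transformation and shows the asymmetry.

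The cost is an edit to one sentence, one title, one header and one footnote, plus one new column. Enrolment, data collection and the analysis stay as they are.

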9.9.2 Sample Size for Safety Analysis

The probability of observing at least 1 vaccine-related SAE depends on the number of participants vaccinated and the underlying incidence rate in the study population. In this study with 80 participants in each vaccination group, there is ≥ 0.90 probability of observing at least 1 vaccine-related SAE in a vaccination group if the incidence of a SAE is $\geq 2.84\%$ ([Table 12](#)).

Table 12 Probability of Observing At Least 1 Vaccine-related Serious Adverse Event in a Group With 80 Participants

Incidence Rate	Probability of ≥ 1 Participant Out of 80 With Vaccine-related SAE
2.84% (1 of every 35 participants)	0.90
3.68% (1 of every 27 participants)	0.95
8.27% (1 of every 12 participants)	0.99

SAE=serious adverse event

If no vaccine-related SAE is observed among the approximately 80 participants in a vaccination group, this study will provide 97.5% confidence that the underlying incidence rate of vaccine-related SAE in that vaccination group is $\leq 4.51\%$ (10 of every 222 individuals).

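### Table 12 pairs an SAE incidence of 8.27% with a probability of 0.99; with 80 participants, 0.99 belongs to 5.59%, and 8.27% belongs to 0.999

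*Combined protocol and SAP*

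**What the plan says.** Section 9.9.2 fixes the group size: "In this study with 80 participants in each vaccination group". Table 12 is titled "Probability of Observing At Least 1 Vaccine-related Serious Adverse Event in a Group With 80 Participants" and has three rows:

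- "2.84% (1 of every 35 participants"), with probability 0.90
- "3.68% (1 of every 27 participants"), with probability 0.95
- "8.27% (1 of every 12 participants"), with probability 0.99

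The text above the table uses the first row as a threshold: the probability is at least 0.90 once the incidence is at least 2.84%. The section closes with a bound for the case of no observed event: "this study will provide 97.5% confidence that the underlying incidence rate of vaccine-related SAE in that vaccination group is" at most 4.51%.

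The Section 9.1 summary refers to Section 9.9.2 for the study's ability to estimate adverse event incidence within each group.

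**The concern.** The step from the second row to the third is too large. With a fixed group size, the incidence needed for a given probability depends on the logarithm of the chance of seeing no event. Going from 0.90 to 0.95 adds 0.84 percentage points (3.68 − 2.84), while going from 0.95 to 0.99 is shown as adding 4.59 (8.27 − 3.68). On the log scale the second step should be only about 2.3 times the first, since ln(5)/ln(2) = 2.32, and not more than 5 times.

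Vaccine-related SAEs are a primary safety endpoint, and Section 9.3 states that nothing is formally tested. Table 12 and the zero-event bound are therefore the only stated properties of the safety sample size. A reader, or the author of the study report, who copies the third row would repeat a wrong one.

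**Working it through.** **Inputs, all from Section 9.9.2:** n = 80 per group; the tabulated quantity is the probability of at least one event; the printed pairs are (2.84%, 0.90), (3.68%, 0.95) and (8.27%, 0.99); the zero-event bound is 4.51% at 97.5% confidence.

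**Formula.** With independent participants and incidence p, the probability of at least one event is P = 1 − (1 − p)^80. The incidence that gives a chosen P is p = 1 − (1 − P)^(1/80).

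**Figures that reproduce**

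- P = 0.90: p = 1 − 0.10^(1/80) = 2.837%, or 1 in 35.2. Printed: 2.84%, 1 in 35.
- P = 0.95: p = 1 − 0.05^(1/80) = 3.675%, or 1 in 27.2. Printed: 3.68%, 1 in 27.
- Zero-event bound: 1 − 0.025^(1/80) = 4.506%. Printed: 4.51%.

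These three matches confirm both the formula and n = 80.

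**The third row**

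- P = 0.99: p = 1 − 0.01^(1/80) = 5.594%, or 1 in 17.9. Printed: 8.27%, 1 in 12.
- In the other direction, at p = 8.27%: P = 1 − 0.9173^80 = 0.9990.
- P = 0.999: p = 1 − 0.001^(1/80) = 8.272%, or 1 in 12.1. This matches both printed forms of the incidence.

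**Other routes to 8.27%.** Each alternative below was solved for the incidence, at P = 0.99 unless another P is stated.

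| Alternative | Incidence |
|---|---|
| Poisson, n = 80 | 5.76% |
| n = 72 | 6.20% |
| n = 70 | 6.37% |
| n = 160 | 2.84% |
| P = 0.995, n = 80 | 6.41% |
| At least 2 events, n = 80 | 8.01% |
| At least 3 events, n = 80 | 10.1% |

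None gives 8.27%. Keeping both 8.27% and 0.99 would require n = ln(0.01)/ln(0.9173) = 53.3 participants, a number the section does not use.

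**Size of the discrepancy.** On the incidence side: 8.27 − 5.59 = 2.68 percentage points, and 8.27/5.59 = 1.48. On the probability side: 0.999 against 0.99, so the chance of seeing no event at 8.27% is 0.10% rather than the 1% implied.

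**The case against.** The strongest reply is that the row does no harm. Under Section 4.2, enrolment of about 160 was set by slow recruitment and the end of vaccine supply, not by Table 12. No analysis, stopping rule or decision uses the third row. The two figures carried into the prose, 2.84% and 4.51%, are correct. The error also runs in the safe direction: an incidence of 8.27% does give a probability of at least 0.99, so the row is true as a lower bound and understates what the study can see. All of this stands, and it keeps the practical impact small.

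It can also be argued that the table only pairs an incidence with a probability, so the literal error is 0.999 printed as 0.99, a difference of 0.009. This is fair as far as it goes. However, the section itself reads the first row as a threshold, and the first two rows are exact thresholds (0.9002 and 0.9502), so a reader will take the third the same way. Rounding does not rescue it, because 0.9990 to two decimals is 1.00. Nor does reading it as a loose bound, because the other rows are not loose.

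Finally, 8.27% and 1 in 12 agree with each other, which suggests that the slip lies in the probability cell. That is likely, but the documents cannot settle it, so both corrections are offered.

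**Conclusion.** The third row of Table 12 is wrong as written. With 80 participants, 0.99 corresponds to an incidence of 5.59% (about 1 in 18), and 8.27% (about 1 in 12) corresponds to 0.999. The conclusion rests only on the section's own n and on the binomial formula that reproduces its other three figures to the printed digit. The error is confined to this row and is conservative. It affects no sample size, analysis or decision. It should be corrected because it misstates a property of the safety sample size in the section to which the plan refers for that purpose.

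**What to change.** Correct the last row of Table 12 in one of two ways:

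- change the incidence to 5.59% (1 of every 18 participants) and keep 0.99, which preserves the sequence 0.90, 0.95, 0.99; or
- keep 8.27% (1 of every 12 participants) and change the probability to 0.999.

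The sponsor should check the source calculation to see which was intended. The rest of Section 9.9.2 needs no change. The cost is one table entry, with no effect on design, conduct or analysis.

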9.10 Subgroup Analyses

There is no subgroup analysis planned to be conducted.

9.11 Compliance (Medication Adherence)

Compliance in this study is defined as receipt of 2 doses of 9vHPV vaccine and mRNA-1273 vaccine in the context of the study. To summarize compliance, the numbers of participants who receive each vaccination will be tabulated. For each vaccination dose, histograms of the time of administration of the vaccine relative to the target vaccination visit will be provided.

9.12 Extent of Exposure

The extent of exposure will be summarized by the number and proportion of study participants administered the 9vHPV vaccine and mRNA-1273 vaccine.

10 SUPPORTING DOCUMENTATION AND OPERATIONAL CONSIDERATIONS

10.1 Appendix 1: Regulatory, Ethical, and Study Oversight Considerations

10.1.1 Code of Conduct for Interventional Clinical Trials

Merck Sharp & Dohme LLC, Rahway, NJ, USA (MSD)

Code of Conduct for Interventional Clinical Trials

I. Introduction

A. Purpose

MSD, through its subsidiaries, conducts clinical trials worldwide to evaluate the safety and effectiveness of our products. As such, we are committed to designing, implementing, conducting, analyzing, and reporting these trials in compliance with the highest ethical and scientific standards. Protection of participants in clinical trials is the overriding concern in the design and conduct of clinical trials. In all cases, MSD clinical trials will be conducted in compliance with local and/or national regulations (including all applicable data protection laws and regulations), and International Council for Harmonisation Good Clinical Practice (ICH GCP), and also in accordance with the ethical principles that have their origin in the Declaration of Helsinki.

B. Scope

Highest ethical and scientific standards shall be endorsed for all clinical interventional investigations sponsored by MSD irrespective of the party (parties) employed for their execution (e.g., contract research organizations, collaborative research efforts). This Code is not intended to apply to trials that are observational in nature, or which are retrospective. Further, this Code does not apply to investigator-initiated trials, which are not under the full control of MSD.

II. Scientific Issues

A. Trial Conduct

1. Trial Design

Except for pilot or estimation trials, clinical trial protocols will be hypothesis-driven to assess safety, efficacy and/or pharmacokinetic or pharmacodynamic indices of MSD or comparator products. Alternatively, MSD may conduct outcomes research trials, trials to assess or validate various endpoint measures, or trials to determine patient preferences, etc.

The design (i.e., participant population, duration, statistical power) must be adequate to address the specific purpose of the trial and shall respect the data

protection rights of all participants, trial site staff and, where applicable, third parties. All trial protocols are and will be assessed for the need and capability to enroll underrepresented groups. Participants must meet protocol entry criteria to be enrolled in the trial.

2. Site Selection

MSD's clinical trials are conducted globally in many different countries and in diverse populations, including people of varying age, race, ethnicity, gender, and accounting for other potential disease-related factors. MSD selects investigative sites based on medical expertise, access to appropriate participants, adequacy of facilities and staff, previous performance in clinical trials, as well as budgetary considerations. Prior to trial initiation, sites are evaluated by MSD personnel (or individuals acting on behalf of MSD) to assess the ability to successfully conduct the trial.

Where appropriate, and in accordance with regulatory authority guidance, MSD will make concerted efforts to raise awareness of clinical trial opportunities in various communities. MSD will seek to engage underrepresented groups and those disproportionately impacted by the disease under study. MSD will support clinical trial investigators to enroll underrepresented groups and expand access to those who will ultimately use the products under investigation.

3. Site Monitoring/Scientific Integrity

Investigative trial sites are monitored to assess compliance with the trial protocol and Good Clinical Practice (GCP). MSD reviews clinical data for accuracy, completeness, and consistency. Data are verified versus source documentation according to standard operating procedures. Per MSD policies and procedures, if potential fraud, scientific/research misconduct, privacy incidents/breaches or Clinical Trial-related Significant Quality Issues are reported, such matters are investigated. When necessary, appropriate corrective and/or preventative actions are defined and regulatory authorities and/or ethics review committees are notified.

B. Publication and Authorship

Regardless of trial outcome, MSD commits to publish the primary and secondary results of its registered trials of marketed products in which treatment is assigned, according to the prespecified plans for data analysis. To the extent scientifically appropriate, MSD seeks to publish the results of other analyses it conducts that are important to patients, physicians, and payers. Some early phase or pilot trials are intended to be hypothesis-generating rather than hypothesis testing; in such cases, publication of results may not be appropriate since the trial may be underpowered and the analyses complicated by statistical issues such as multiplicity.

MSD's policy on authorship is consistent with the recommendations published by the International Committee of Medical Journal Editors (ICMJE). In summary,

authorship should reflect significant contribution to the design and conduct of the trial, performance or interpretation of the analysis, and/or writing of the manuscript. All named authors must be able to defend the trial results and conclusions. MSD funding of a trial will be acknowledged in publications.

III. Participant Protection

A. Regulatory Authority and Ethics Committee Review (Institutional Review Board [IRB]/Independent Ethics Committee [IEC])

All protocols and protocol amendments will be submitted by MSD for regulatory authority acceptance/authorization prior to implementation of the trial or amendment, in compliance with local and/or national regulations.

The protocol, protocol amendment(s), informed consent form, investigator's brochure, and other relevant trial documents must be reviewed and approved by an IRB/IEC before being implemented at each site, in compliance with local and/or national regulations. Changes to the protocol that are required urgently to eliminate an immediate hazard and to protect participant safety may be enacted in anticipation of ethics committee approval. MSD will inform regulatory authorities of such new measures to protect participant safety, in compliance with local and/or national regulations.

B. Safety

The guiding principle in decision-making in clinical trials is that participant welfare is of primary importance. Potential participants will be informed of the risks and benefits of, as well as alternatives to, trial participation. At a minimum, trial designs will take into account the local standard of care.

All participation in MSD clinical trials is voluntary. Participants enter the trial only after informed consent is obtained. Participants may withdraw from an MSD trial at any time, without any influence on their access to, or receipt of, medical care that may otherwise be available to them.

C. Confidentiality

MSD is committed to safeguarding participant confidentiality, to the greatest extent possible, as well as all applicable data protection rights. Unless required by law, only the investigator, Sponsor (or individuals acting on behalf of MSD), ethics committee, and/or regulatory authorities will have access to confidential medical records that might identify the participant by name.

D. Genomic Research

Genomic research will only be conducted in accordance with a protocol and informed consent authorized by an ethics committee.

IV. Financial Considerations

A. Payments to Investigators

Clinical trials are time- and labor-intensive. It is MSD's policy to compensate investigators (or the sponsoring institution) in a fair manner for the work performed in support of MSD trials. MSD does not pay incentives to enroll participants in its trials. However, when enrollment is particularly challenging, additional payments may be made to compensate for the time spent in extra recruiting efforts.

MSD does not pay for participant referrals. However, MSD may compensate referring physicians for time spent on chart review and medical evaluation to identify potentially eligible participants.

B. Clinical Research Funding

Informed consent forms will disclose that the trial is sponsored by MSD, and that the investigator or sponsoring institution is being paid or provided a grant for performing the trial. However, the local ethics committee may wish to alter the wording of the disclosure statement to be consistent with financial practices at that institution. As noted above, all publications resulting from MSD trials will indicate MSD as a source of funding.

C. Funding for Travel and Other Requests

Funding of travel by investigators and support staff (e.g., to scientific meetings, investigator meetings, etc.) will be consistent with local guidelines and practices.

V. Investigator Commitment

Investigators will be expected to review MSD's Code of Conduct as an appendix to the trial protocol, and in signing the protocol, agree to support these ethical and scientific standards.

